3.6 Participants

The total sample size for this study will be 60 participants administering the test. There will be 4 user groups. A breakdown of composition of each group is detailed Table 4.

Table 4 - Study sample

User groups	Sample size
Adolescents between the age of 12 and 17	15
Adults aged 18+	15
Adults administering the test to an adult dependant	15 caregivers plus 15 dependants
Adults administering the test to a child under the age of 12	15 parents plus 15 children

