Use step 8 Holding the swab between your fingers, open your mouth wide and rub the fabric tip of the swab over both tonsils (or where they would have been). Do this with firm contact 4 times on each side (use a mirror to help you do this). Carefully remove the swab from the back of your throat.	Participant rubs the fabric/soft tip of swab over both tonsils (or where they would be if they have been removed) with at least 4 observable directional movements.
	Participant removes the swab from their throat without touching any part of their mouth at this stage (not touching tongue, teeth, cheeks, gums etc)

Use step 9 Put the same swab gently into one nostril until you feel a slight resistance (about 2.5cm up your nose). Roll the swab firmly around the inside of the nostril, making 10 complete circles.	Participant puts the same swab fabric/soft tip into one nostril about 2.5 cm up nostril. Participant rolls the swab around the circumference of their nostril in full circles at least 10 times. Participant then places the same swab fabric/ soft tip into the other nostril about 2.5 cm up nostril. Participant rolls the swab around the circumference of
	the other nostril in full circles at least 10 times.
Process the swab sample	
Use step 10 Remove the extraction tube from the cup and place the fabric tip of the swab into the extraction tube so it is in the fluid. Press the tip against the edge of the extraction tube with force, while rotating it around the tube for 15 seconds.	Participant places the fabric/soft tip of the swab into the extraction tube. Participant presses the fabric/soft tip of the swab against the side of the extraction tube with force while rotating the swab around the extraction tube for 15 seconds.
Use step 11 Pinch the tube as you remove the swab to make sure that all the fluid is removed from the soft tip of the swab. Place the swab in the plastic waste bag provided.	Participant takes out the swab whilst squeezing the extraction tube and fabric/soft tip of the swab (to squeeze as much fluid out of swab as possible). Participant puts the swab into a plastic bag and disposes of it into their household rubbish.
Use step 12 Press the nozzle cap tightly on to the extraction tube to avoid any leaks	Participant presses the nozzle cap tightly onto the extraction tube (to avoid leaks).

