4.5 Simulated use caregivers of paediatrics and dependents

Participants will be asked to open the pack and to follow the steps of use presented to them to perform the test on their child/ dependent.

The simulated use steps to be observed are as follows in table 8:

Table 8 - Use	Steps for	adult testing	a child	or dependent

Use Step	Acceptance criteria
Repeat Use Steps 1 through 7 as per Section 4.4.1 (table 7) of this protocol, then proceed with Use Steps 8 and 9 below.	As per section 4.4.1 (table 7)
Use step 8 (child/dependant) Ask the child to open their mouth wide, then rub the fabric tip of the swab over both tonsils (or where they would have been). Do this with firm contact 4 times on each side. Carefully remove the swab. If you cannot swab the tonsils, you can swab both nostrils.	Participant rubs the fabric tip of the swab over both tonsils with firm contact 4 times on each side, without touching any part of the child/ dependent's mouth at this stage (not touching tongue, teeth, cheeks, gums etc). Participant removes the swab from the child/dependent's throat without touching any part of their mouth at this stage (not touching tongue, teeth, cheeks, gums etc)
Use Step 9 (child/dependent) Put the fabric tip of the same swab gently into one of their	Participant puts the fabric tip of the same swab gently into one of their nostrils Participant rolls the swab firmly
nostrils until you feel some resistance. Roll the swab firmly around the inside of the nostril, making 10 complete circles and slowly remove it. If you could not swab	around the inside of the nostril, making 10 complete circles and slowly removes it.
their throat repeat in their other nostril.	If the user could not swab the throat, they repeat in the other nostril.
Repeat Use Steps 10 through 14 , as per Section 4.4.1 (table 7) of this protocol.	As per section 4.4.1 (table 7)

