WHILE WAITING FOR THE TEST RESULTS PROCEED WITH 6.5

NOTE TO MODERATOR: RECORD CURRENT TIME AND SET A TIMER FOR 30 MINUTES.

6.4 **CAREGIVER** Simulated use and Root Cause (40 mins)

The test-kit that you are going to use today is detects the presence of COVID-19. You would use this test-kit on yourself or someone you care for, and it would be posted to your home as part of the UK Government's Test and Trace scheme.

I now want you to imagine that you have been sent the test kit and it's time to perform the test on your child/family member. Remember this is a real test which is going to give you a real result, so please do everything you would do if I weren't here today. Once you have finished let me know and I will ask you some questions.

When giving yourself the test, please refer to the instructions provided to you in the kit.

Do you have any questions before we start?

You may now proceed to do the test.

REFERRED TO IFU? YES / NO

Use Step/Acceptance criteria	Use Error	Use Difficulty	Close Call	Pass	Comments
Clear, clean and dry a flat surface to place the home test kit on.					
Wash your hands thoroughly for 20 seconds, using soap and warm water, or hand sanitiser.					
Take the test kit out of the foil packaging and place it onto the cleaned flat surface.					
Setup your test					
Use Step 1 Carefully twist or snap open the sachet					
Use Step 2 Pour all of the fluid from the sachet into the extraction tube.					

Use Step/Acceptance criteria	Use Error	Use Difficulty	Close Call	Pass	Comments
Use Step 3 Place the filled tube in a cup or container to avoid spilling it while you use the swab					
Use Step 4 Check the swab in the sealed wrapper in front of you					
Use step 5 (Not required for non self test) Gently blow your nose into a tissue.					
Use step 6 Wash and dry your hands again (or use sanitiser if this is available).					
Use Step 7 Open the swab package and gently take out the swab.					
Take your swab sample					
Use step 8 (child/dependant) Ask the child to open their mouth wide, then rub the fabric tip of the swab over both tonsils (or where they would have been). Do this with firm contact 4 times on each side. Carefully remove the swab. If you cannot swab the tonsils, you can swab both nostrils.					

Use Step/Acceptance criteria	Use Error	Use Difficulty	Close Call	Pass	Comments
Use Step 9 (child/dependent)					
Put the fabric tip of the same swab gently into one of their nostrils until you feel some resistance.					

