Roll the swab firmly around the inside of the nostril, making 10 complete circles and slowly remove it. If you could not swab their throat repeat in their other nostril.					
Process the swab sample					
Use step 10					
Remove the extraction tube from the cup and place the fabric tip of the swab into the extraction tube so it is in the fluid.					
Press the tip against the edge of the extraction tube with force, while rotating it around the tube for 15 seconds.					
Use step 11					
Pinch the tube as you remove the swab to make sure that all the fluid is removed from the soft tip of the swab.					
Place the swab in the plastic waste bag provided.					
Use step 12					
Press the nozzle cap tightly on to the extraction tube to avoid any leaks					

Use Step/Acceptance criteria	Use Error	Use Difficulty	Close Call	Pass	Comments
Use step 13 Gently squeeze the extraction tube to place 2 drops of liquid onto the specimen well on the test strip.					
Use step 14 Place the test strip here (Optional). Check the time or set a timer if you have one. Wait 30 minutes to read your result.					

START TIMER (30 minutes)

NOTE TO MODERATOR: AFTER STEP 14 ASK THE PARTICIPANT HOW LONG THEY SHOULD WAIT TO READ THE RESULTS

Wait full 30 minutes before reading results. A positive result can appear at any time after 20 minutes, however you must wait for a full 30 minutes to record a negative result as the test line may take longer to appear.

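### The protocol's scoring texts contradict each other at steps 9, 5 and 11, so the same behaviour can fail or pass depending on which page is applied

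*Protocol*

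**What the plan says.** **Step 9, self-test.** The step column of Table 7 (section 4.4.1) reads "Put the same swab gently into one nostril until you feel a slight resistance (about 2.5cm up your nose", followed by ten circles in that nostril. The criterion in the same row asks for that and then continues: "Participant then places the same swab fabric/ soft tip into the other nostril about 2.5 cm up nostril", again with at least ten circles. The score sheet in Appendix 10, section 6.3.1, has a column headed Use Step/Acceptance criteria, but it holds only the one-nostril step text.

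**Step 9, caregivers.** Table 8 (section 4.5) makes the second nostril conditional: "If the user could not swab the throat, they repeat in the other nostril". Here step and criterion agree.

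**Step 5, caregivers.** Table 8 begins "Repeat Use Steps 1 through 7 as per Section 4.4.1 (table 7) of this protocol", with the Table 7 criteria. For step 5 that criterion is that the participant blows their nose. The caregiver score sheet (Appendix 10, section 6.4) labels the same step "Use step 5 (Not required for non self test".

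**Step 11, everyone.** The step text stops at placing the swab in the waste bag. The criterion goes further: "Participant puts the swab into a plastic bag and disposes of it into their household rubbish". Section 7 of the IFU (Appendix 1) places disposal in household waste after the test is complete.

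**Which text governs.** Section 4.4 says that the success and use-error criteria are found in both the discussion guide and the protocol section. Section 4.11 says that outcomes are classified by Table 10.

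**The concern.** The objective in section 2.2 is to validate safe and effective use, and the step scores are main performance data for it. A self-tester who does exactly what the step 9 text says cannot meet the Table 7 criterion, yet has done everything the sheet shows. A caregiver who does not blow their nose misses the criterion that Table 8 imports and meets the sheet. Two scorers working from different pages would report different results for the same recording. Under Table 10 each Use Error also triggers a root cause investigation, so an error produced by the criterion could be investigated as a fault of the IFU or the kit.

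**Working it through.** The plan derives no figure on this point. The check sets the texts side by side and then counts who is affected.

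**Inputs.** Section 3.6: "The total sample size for this study will be 60 participants administering the test". Table 4 gives four groups of 15, and 4 × 15 = 60 agrees with the stated total. Self-testers: 15 adolescents + 15 adults = 30. Caregivers: 15 testing a child + 15 testing an adult dependant = 30.

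**Comparison of texts.**

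| Step | Protocol table criterion | Score sheet, Appendix 10 | Participants |
|---|---|---|---|
| 9, self-test | both nostrils (Table 7) | one nostril | 30 |
| 5, caregiver | participant blows nose (Table 8, from Table 7) | not required | 30 |
| 11 | waste bag, then household rubbish (Table 7; Table 8 repeats steps 10 to 14) | waste bag only | 60 |

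**Does anything settle which text governs?**
- Section 4.4 locates the criteria in two places, and the step tables of the guide hold step text without the separate criteria. It also cites Appendix 6 and section 4.1.1, whereas the guide is headed Appendix 10 and the criteria stand in section 4.4.1.
- Table 10 defines a Use Error by an unintended result, including inability to complete a task, certain deviations from the IFU, and need for assistance. An unmet acceptance criterion is not named.
- The sessions are recorded (section 4.10), which preserves the behaviour but not the rule for scoring it.

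**Worst case at step 9.** If all 30 self-testers do only the printed step:
- Table 7 criterion: 30/30 = 100% miss it (exact 95% interval 88.4% to 100%).
- Score sheet: 0/30 = 0% fail (exact 95% interval 0% to 11.6%).

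The two intervals describe identical behaviour. The same 30/30 against 0/30 holds at step 5 if no caregiver blows their nose.

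**Other shares at step 9.** The documents do not give the share *f* of self-testers who swab one nostril only, so a range is assumed. Expected misses = 30 × *f*; chance of at least one miss = 1 − (1 − *f*)^30.

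| Assumed *f* | Expected misses of 30 | Chance of at least one |
|---|---|---|
| 10% | 3 | 1 − 0.9^30 = 95.8% |
| 25% | 7.5 | above 99.9% |
| 50% | 15 | above 99.9% |
| 100% | 30 | 100% |

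Under the score sheet the count from this cause is 0 in every row. Once table, criterion and sheet describe the same act, the two counts coincide.

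**The case against.** **Final classification follows Table 10, not the acceptance criteria.** This stands in part. A reader might infer that participants who follow the steps will be recorded as Use Errors. The documents do not establish that: Table 10 does not make an unmet criterion a Use Error, and the sheet would pass the same act. But section 4.4 does call the criteria success and use-error criteria, so the score is undetermined, not safely a pass.

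**Compliance with the IFU at step 9 cannot be checked.** This stands. The swabbing page is not legible in Appendix 1 as available, so the IFU may or may not mention a second nostril. The mismatch shown is between the protocol's own step column, its criterion and its score sheet.

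**Step 5 does contain nose blowing.** Correct. Its step text and criterion match for self-testers. The conflict is only whether the step applies to caregivers.

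**Step 11 is largely a matter of timing.** Mostly correct. A participant who follows the IFU to its end does put the kit in household waste, which is why this is the lesser point.

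**Two further inferences do not hold.** The caregiver sheet's step 14 wording, "Place the test strip here (Optional", may look like a conflict with the flat surface in Table 7, but an optional spot and a flat surface can be different things. The conditional second nostril in Table 8 does not show that Table 7 is wrong, because it belongs to a separate caregiver procedure.

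**The step score is not the only scored outcome.** Correct. The knowledge questions (section 4.6) and the result reading (Appendix 10, section 6.7) are also judged against right answers, and Use Difficulty is recorded separately.

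**Conclusion.** The contradictions at step 9 (Table 7 within its own row, and against the self-test sheet) and step 5 (Table 8 against the caregiver sheet) are real. Between them they reach all 60 participants: 30 at step 9 and the other 30 at step 5. As written, the score at these steps depends on the page the scorer uses. Step 11 is a smaller mismatch of the same kind.

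The difference of 30/30 against 0/30 is a worst case, not an estimate. It assumes that every self-tester swabs one nostril only, or that no caregiver blows their nose, and the documents give neither share. At step 9 even an assumed 10% share makes at least one affected score very likely (95.8%). The conclusion rests on the protocol's own texts and makes no claim about what the swabbing page of the IFU says.

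**What to change.** Before the first session:

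1. Reconcile step text, acceptance criterion, score sheet and IFU for steps 9, 5 and 11, so that all carry one rule for each user group. Those responsible for the IFU must decide which sampling instruction stands; no view is taken here.
2. Print the reconciled criteria on both score sheets in Appendix 10, and correct the references in section 4.4 so that they lead to them.
3. State in Table 10 how an unmet acceptance criterion is scored.
4. Have the observer log, from the video already planned, the number of nostrils swabbed and the circles in each. The reconciled rule can then be applied uniformly wherever the act is in view.

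The cost is wording changes to Tables 7, 8 and 10, section 4.4 and the two sheets (and to the IFU if the reconciliation calls for it), plus two extra counts per session. Sample size and session length do not change.

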4.5 Simulated use caregivers of paediatrics and dependents

Participants will be asked to open the pack and to follow the steps of use presented to them to perform the test on their child/ dependent.

The simulated use steps to be observed are as follows in table 8:

Table 8 - Use	Steps for	adult testing	a child	or dependent

Use Step	Acceptance criteria
Repeat Use Steps 1 through 7 as per Section 4.4.1 (table 7) of this protocol, then proceed with Use Steps 8 and 9 below.	As per section 4.4.1 (table 7)
Use step 8 (child/dependant) Ask the child to open their mouth wide, then rub the fabric tip of the swab over both tonsils (or where they would have been). Do this with firm contact 4 times on each side. Carefully remove the swab. If you cannot swab the tonsils, you can swab both nostrils.	Participant rubs the fabric tip of the swab over both tonsils with firm contact 4 times on each side, without touching any part of the child/ dependent's mouth at this stage (not touching tongue, teeth, cheeks, gums etc). Participant removes the swab from the child/dependent's throat without touching any part of their mouth at this stage (not touching tongue, teeth, cheeks, gums etc)
Use Step 9 (child/dependent) Put the fabric tip of the same swab gently into one of their	Participant puts the fabric tip of the same swab gently into one of their nostrils Participant rolls the swab firmly
nostrils until you feel some resistance. Roll the swab firmly around the inside of the nostril, making 10 complete circles and slowly remove it. If you could not swab	around the inside of the nostril, making 10 complete circles and slowly removes it.
their throat repeat in their other nostril.	If the user could not swab the throat, they repeat in the other nostril.
Repeat Use Steps 10 through 14 , as per Section 4.4.1 (table 7) of this protocol.	As per section 4.4.1 (table 7)

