4.4 Simulated use adult and adolescents

Participants will be asked to open the pack and to follow the steps of use presented to them.

The moderator will observe the participant complete the steps of use. To ensure the task is representative of a real-use scenario, the moderator will not interact with the participant during this task and will not offer help to the participant. The moderator will only verbally interject if the participant gives up on the task, or if the moderator foresees a dangerous scenario developing. A list of tasks and their success/use-error criteria are found in the discussion guide Appendix 6 and section 4.1.1

During the simulated use participants are expected to undertake all steps as described in the IFU to perform a self-test using the LFD test kit.

This task begins with all the study components in their unopened form on the table and ends with the participant indicating that they have done everything they would do at home to perform the test.

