4.11 Analyses

After all sessions are completed, the collected data will be analysed to determine if the task performance was a success, use error, close call, or use difficulty, as per the criteria defined in Table 10. Root cause analysis will be conducted on all tasks where use errors, close calls, and use difficulties were present. This analysis will draw upon study video data, participant responses from post-task interviews, and expert review of the use problem.

Outcome	Definition	Root Cause Investigation Required?	Method of Scoring Data
Success	Participant performs the task correctly on the initial attempt without assistance	No	Success Close Call Use Error N/A

Table	10 -	Scoring	definitions
-------	------	---------	-------------

Outcome	Definition	Root Cause Investigation Required?	Method of Scoring Data
Close Call	 Any instance in which a participant makes a use error e.g. by attempting to undertake an action without accurate reference to the IFU, but then retries resulting in a successful completion of a user step. This outcome also considers: The user verbally expresses frustration or facial expressions and body postures indicate frustration when using the device; The user re-reads the same section of the IFU during a task, in an attempt to comprehend a sequence of steps use The user is able to accomplish a task or step, but experiences frustration or discomfort in the process of doing so. 	Yes	Success Close Call Use Error N/A
Use Error	 Any action or lack of action while using the packaging that leads to a different result than that intended by the manufacturer or expected by the user, including: A participant's inability to complete a task; A deviation from the IFU that leads to a device response that is different than intended or expected by the participant; An instance where the participant requires assistance from study personnel to advance through tasks. The following will not be considered use errors: A malfunction of the packaging that causes an unexpected result. 	Yes	Success Close Call Use Error N/A

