Use Difficulty	 Any observed difficulty on the part of the user while performing the test, which does not result in a use error, but points to an underlying usability concern with the IFU or test kit, Examples include (but are not limited to): The user verbally expresses frustration or facial expressions and body postures indicate frustration when using the packaging; The user re-reads the same section of the IFU during a task, in an attempt to comprehend a sequence of steps The user is able to apply the required amount of force or dexterity to accomplish a task or step with the kit, but experiences frustration or discomfort in the process of doing so. 	Yes	Yes/No This metric is collected in addition to the observational score of Success/Close Call/Use Error

Outcome	Definition	Root Cause Investigation Required?	Method of Scoring Data
N/A	If a task cannot be completed for a reason out of the control of the participant, the task should be scored as N/A. While root cause investigation is not required, notes need to be collected to indicate the reason for scoring N/A. Some examples include: • Packaging failure	No	Success Close Call Use Error N/A

5 Study considerations

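### Caregiver Step 8 permits a nostrils-only route that its own acceptance criterion cannot pass, so correct use risks a false use error and inconsistent scoring

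*Protocol*

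**What the plan says.** Protocol section 4.5, Table 8, sets the caregiver version of Steps 8 and 9.

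- **Step 8 instruction.** After describing the tonsil swab, it adds: "If you cannot swab the tonsils, you can swab both nostrils".
- **Step 8 acceptance criterion.** It has two parts: "Participant rubs the fabric tip of the swab over both tonsils with firm contact 4 times on each side", and then "Participant removes the swab from the child/dependent's throat without touching any part of their mouth at this stage". Neither mentions the alternative.
- **Step 9 acceptance criterion.** It does carry the alternative: "If the user could not swab the throat, they repeat in the other nostril".

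Section 4.4, written for the self-test groups, explains the status of such criteria: "A list of tasks and their success/use-error criteria are found in the discussion guide". Section 4.11, Table 10, defines the scores. Success is "Participant performs the task correctly on the initial attempt without assistance". Use Error includes "A participant's inability to complete a task". For N/A the rule is: "If a task cannot be completed for a reason out of the control of the participant, the task should be scored as N/A".

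The caregiver score sheet in section 6.4 of the discussion guide prints the Step 8 instruction, alternative included, but not the Table 8 criterion. Its columns are Use Error, Use Difficulty, Close Call, Pass and Comments.

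**The concern.** The instruction and the criterion in the same table row disagree about what counts as doing Step 8 properly. The instruction accepts two routes and the criterion accepts one. The study is meant to show whether the IFU lets ordinary users carry out the test, so a participant who does what the IFU allows should not be charged with a failure.

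Two things are at stake. The first is a false use error held against the IFU when its own instruction was followed. The second is consistency: if scorers resolve the disagreement differently, identical behaviour receives different scores, and Step 8 results in the two caregiver groups partly reflect who did the scoring.

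**Working it through.** **1. Exposure.** Section 3.6 (Table 4) gives four groups of 15 people administering the test: 4 × 15 = 60, which reproduces the stated total. Table 8 applies to the two caregiver groups, so 2 × 15 = 30 sessions are scored against this criterion.

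**2. The permitted route set against each criterion.** Take a caregiver who cannot swab the tonsils and then swabs both nostrils as the IFU allows.

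| Item | Does the permitted route satisfy it? |
|---|---|
| Step 8 instruction | Yes, named as an alternative |
| Step 8 criterion, tonsil contact | No, cannot be met |
| Step 8 criterion, removal from the throat | No, presupposes a throat swab |
| Step 9 criterion | Yes, has a branch for it |

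The gap is confined to Step 8. The Step 9 branch says how Step 9 is judged, not how Step 8 is scored when that branch applies.

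**3. What Table 10 would do with it.** Four scores are arguable:

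- Use Error, because the task as the criterion defines it was not completed.
- Close Call, if an unsuccessful attempt at the throat followed by completion through the nostrils is treated as a recovered error.
- N/A, if a child's or dependant's inability is outside the caregiver's control. The section 6.4 sheet has nowhere to enter it.
- Success, if correct performance is judged against the instruction rather than the criterion.

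A moderator working from the section 6.4 sheet alone sees the instruction and may tick Pass. An analyst working from Table 8 may record Use Error for the same session.

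**4. Size per case.** If k otherwise correct caregivers in a group of 15 use the permitted route and are scored Use Error, Step 8 success is (15 − k)/15. Over both groups it is (30 − k)/30.

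- k = 1: 14/15 = 93.3%; 29/30 = 96.7%.
- k = 3: 12/15 = 80.0%; 27/30 = 90.0%.

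Scored as Success, the same sessions give 15/15 and 30/30.

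**5. Is at least one case likely?** The documents give no rate, so p is an assumption. The chance of one or more cases among n caregivers is 1 − (1 − p)^n.

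| Assumed p | n = 15 | n = 30 | Expected cases in 30 |
|---|---|---|---|
| 5% | 53.7% | 78.5% | 1.5 |
| 10% | 79.4% | 95.8% | 3 |
| 20% | 96.5% | 99.9% | 6 |

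Even at the lowest assumed rate, the scoring question would probably arise at least once.

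**The case against.** The strongest reply is that the alternative is assessed where it is performed, in Step 9. A route printed in the IFU is intended by the manufacturer, so under the leading definition in Table 10 it is not a use error at all, and an experienced moderator would score it as Success. This stands to the extent that the direction of mis-scoring is not fixed. A reader might infer that these caregivers will certainly be scored as failures; Table 10 does not support that. What remains is that reaching Success means setting aside the written Step 8 criterion, and nothing tells the scorer to do so.

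Three further inferences are tempting and also go too far.

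- **That a caregiver who could not swab the throat cannot be told apart from one who skipped it.** Sessions are one-to-one and observed live (sections 3.1 and 3.2), video-recorded with notes taken (section 4.10), and scored on a sheet with a Comments column. Section 6.5 probes difficulties, and Table 10 requires a noted reason for N/A. The information can be recovered. What is missing is a set place to record the route and a rule for scoring it.
- **That difficult cases would drop out of the Step 8 denominator.** The protocol states no success percentage, pass threshold or rule for how N/A enters a rate. Such rules are commonly left to the analysis plan, which is not at hand.
- **That Step 8 success would be badly depressed.** Any large figure rests on an assumed share of subjects who cannot be throat-swabbed. The screener in Appendix 3 does not recruit children under 4 and asks caregivers whether they are willing to perform the test, so the number may be small. Thirty is the number exposed, not the number affected.

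**Conclusion.** The point holds as a contradiction within one row of Table 8. The Step 8 criterion cannot be met by a caregiver who follows an alternative that the Step 8 instruction permits and the Step 9 criterion recognises. This is not detail awaiting an analysis plan: the protocol itself fixes the criterion, and applied literally it gives the wrong score. The consequence is a risk of false use errors and of inconsistent scoring in the 30 caregiver sessions.

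Each case scored as a use error costs 1/15 (6.7 percentage points) of a group's Step 8 success. That figure assumes the other caregivers in the group succeed or fail independently of this scoring choice, and that success is reported over all 15. The number of cases cannot be derived from the documents. The conclusion does not depend on it, and takes no position on which swabbing rule is right.

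**What to change.** Reconcile the Step 8 criterion in Table 8 with its own instruction and with Step 9:

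1. Add a branch to the Step 8 criterion: a caregiver who could not swab the tonsils and swabs both nostrils as instructed has followed the IFU and is scored Success, not Use Error or N/A. Keep the condition as the instruction has it (could not), without adding a requirement that the throat was attempted, which the documents do not contain.
2. On the section 6.4 score sheet, add an entry for the route taken: throat plus nostril, or nostrils only with the reason. The Step 8 and Step 9 branches are then applied from the same record.
3. Report the nostrils-only count for each caregiver group beside the Step 8 results, so that readers can see how many successes came by each route.

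The cost is one tick-box and one line of criteria. Sample size and session length do not change.
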